### 10.4. Primary Analysis

The rate of completion of the primary outcome - housing situation via the RTLFB inventory will be reported at each follow-up time point (baseline, 3 and 6 months). In service users providing valid data, we will summarise their housing situation using frequencies and proportions in three ways:

- Level 1: Categorical outcome – homeless, not homeless, institution
- Level 2: Categorical outcome – rough sleeping, temporary and/or unstable, hidden, institution, stable but insecure, stable and secure
- Level 3: Categorical outcome - all twelve categories (A1 to E12)

See Appendix C for the coding of the outcomes.

If a service user reports to be in an institution (e.g. prison, probation facility, hospital or asylum support accommodation) at the time of follow-up, they are neither defined as homeless or not homeless. For this reason, we will use the additional definition of homelessness developed by RTLFB Inventory of 'functional homelessness'. The RTLFB Inventory developed rules that detailed when an institutional setting would be considered functional homelessness e.g., a psychiatric hospitalisation (institutional setting) would not be considered functionally homeless if a service user was living in a stable setting (i.e. not homeless) prior to the hospitalisation and returned there once discharged. However, if the service user was rough sleeping prior to hospitalisation and returned to the street upon discharge, then they would be considered functionally homeless for that entire duration. For this reason, if a service user reports to be in an institution at the time of follow-up we will take their previous housing situation for the purpose of the analysis; this will be used for of all levels of categorisation.

The primary analysis will use a multilevel (two levels) mixed-effects generalised linear modelling technique to examine the intervention effect on Level 2 categorisation of housing situation at 6 months.

The model will contain the trial arm as a main fixed effect, will adjust for LAs RSI funding allocation 2022-2025, and will account for the nesting (random-effect) of service users within LA, resulting in observations within the same cluster likely to be correlated (ignoring this can lead to underestimated standard errors and overstated statistical significance). We will not adjust for baseline measure as all service users will be rough sleeping. A general equation of

the multilevel mixed-effects generalised linear model for our analysis can be described as follows:

$$g(y|X, u) = X\beta + Zu + \varepsilon$$

The fitted model can be formulated as bellow:

$$g\{E(y|X, u)\} = X\beta + Zu$$

where:

- $y \sim F$  (i.e., the outcome  $y$  follows a distribution  $F$  (e.g., normal, binomial, ordinal etc.))
- $y$  is the ( $n \times 1$ ) vector of responses from the distribution  $F$  such as for the outcome level 1, it takes values as (1=stable but secure), (2=stable but insecure), (3=hidden, temporary and/or unstable), (4=rough sleeping).
- $X\beta + Zu = \eta$  is called a linear predictor and its terms are described as below:
- $X$  is an ( $n \times p$ ) design/covariate matrix for the fixed effects  $\beta$  including the study arms (intervention=1 versus control=0) and LAs RSI funding allocation 2022-2025 strata (e.g., 0=low RSI funding allocation, 1=high RSI funding allocation) and other baseline covariates such as service users' age and gender.
- $Z$  is the ( $n \times q$ ) design/covariate matrix for the random effects  $u$  assumed to be normally distributed with mean 0 and ( $q \times q$ ) variance matrix ( $\Sigma$ ). In this study, it may be kept limited to the random effect of local authority (clusters) only matrix  $\Sigma$ .

The effect size will be reported as an absolute risk differences (intervention minus control) alongside 95% CIs, at each time point. Adjusted relative risk ratios for intervention versus control will be computed from the model presented alongside 95% CI. We will also estimate the clustering of outcomes by trial arm via intra-cluster correlation coefficients (with 95% CIs). The effect estimates will be used for the sample size calculation of a future definitive study.

For analysis of the Level 1 outcome, the outcome will be a binary outcome (homeless=0 vs not homeless=1) and a mixed effect logistic regression model, with the assumption of binomial distribution, will be used to compute the point estimate as relative risk ratios alongside 95% CI.

For the categorical (ordinal) outcome of Level 3 all twelve categories (A1 to E12) will be included. The mixed-effects generalised linear model will be fitted with the assumption of ordinal distribution, a logistic link function and a suitable linear predictor  $\eta$  including a random effect of the Local Authority. In all analyses, model assumption will be evaluated to insure a best fit of the model.

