## 5.2. Study Design

### 5.2.1. Two-arm pilot cluster randomised controlled trial

The study design is a two-arm pilot cluster randomised controlled trial (cRCT). Local Authorities (LAs) are the unit of randomisation. 16 eligible LAs will be randomly assigned by an independent statistician in a 1:1 ratio (8 LAs per arm) to receive funding to embed a health professional as part of the outreach team (a qualified nurse) or remain with their usual practice.

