## 9. SAMPLE SIZE AND POWER CALCULATION

### 9.1. Sample Size / Power Calculation

The aim of this pilot cRCT is to evaluate feasibility and acceptability of outreach services with a health specialism for people rough sleeping and provide indicative evidence of its effectiveness. The study will determine numbers of service users eligible for routine data collection and response rates, estimates of effect sizes and intra-cluster correlation coefficients as well as providing in-depth knowledge on the views and experiences of health outreach workers and people who received care.

A sample size calculation was provided by CHI based on the number of LAs and service users that could viably be engaged within the time and budget available. The sample size was based on 80% power, 5% alpha, a minimum detectable effect size (MDES) of 0.53, an average cluster size (LA) of 40 service users, ICC of 0.1, allocation ratio 1:1, and 10% attrition (Table 10). We therefore aim to randomise 16 clusters (LAs) with 8 to receive funding to embed a health professional as part of the outreach team (a qualified nurse) and 8 to remain with their usual practice, with a total of 711 LA service users required in total.

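### Section 10.4 plans intra-cluster correlations only by trial arm, from eight Local Authorities each; one pooled, adjusted estimate from all 16 would be more precise at almost no cost

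*Protocol*

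**What the plan says.** Protocol 10.4 gives the only instruction on estimating the ICC: "We will also estimate the clustering of outcomes by trial arm via intra-cluster correlation coefficients (with 95% CIs". Section 5.2.1 fixes the number of clusters: "16 eligible LAs will be randomly assigned by an independent statistician in a 1:1 ratio (8 LAs per arm".

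Section 9.1 lists what the pilot will determine, including "estimates of effect sizes and intra-cluster correlation coefficients". It does not say whether these are by arm or pooled.

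The primary model in 10.4 is one two-level model fitted to both arms, with arm and RSI funding as fixed effects. Of its random part the protocol says "In this study, it may be kept limited to the random effect of local authority (clusters) only". No arm-specific variance is described.

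On what feeds the next trial, 10.4 says "The effect estimates will be used for the sample size calculation of a future definitive study". That sentence does not mention the ICC.

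**The concern.** The size of a cluster trial depends directly on the ICC through the design effect, so it is one of the most useful numbers a pilot can leave behind. An ICC estimated from eight clusters has only seven between-cluster degrees of freedom. Splitting the estimate by arm, with no pooled figure beside it, gives up about half of the information that the same data hold.

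The by-arm plan also does not follow directly from the stated model. A single LA random effect common to both arms gives one between-LA variance. Two ICCs would need separate fits or arm-specific variances. As written, the plan asks for the less precise quantity and does not name the one that its own model supplies. A reader planning a definitive trial could be left with two imprecise values and no stated choice between them.

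**Working it through.** **Inputs.** Section 9.1 and Table 10 of the protocol give "80% power, 5% alpha, a minimum detectable effect size (MDES) of 0.53, an average cluster size (LA) of 40 service users, ICC of 0.1", a two-sided test, 8 clusters per arm and 10% individual attrition. The protocol states no CI for the ICC.

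**The plan's own figures first.** The design effect is 1 + 39 × 0.10 = 4.9. The minimum detectable effect is (t at 0.975 + t at 0.80) × √(2 × 4.9 / (8 × 40)). The square root is √0.030625 = 0.175. On 13 df this gives (2.160 + 0.870) × 0.175 = 0.530, and on 14 df it gives 0.527. Both round to the stated 0.53. The total is 640 / 0.9 = 711, as stated. The planning inputs are therefore usable as they stand.

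**Interval for the ICC.** I used the exact F interval for a one-way analysis-of-variance ICC with equal clusters of size m:

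- F = [1 + (m − 1) × ICC] / (1 − ICC) = 4.9 / 0.9 = 5.444 at ICC 0.10 and m = 40.
- Lower limit: (F/F₀.₉₇₅ − 1) / (F/F₀.₉₇₅ + m − 1). The upper limit uses F₀.₀₂₅ in the same way.

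| Estimate | df | F₀.₉₇₅, F₀.₀₂₅ | 95% CI |
|---|---|---|---|
| One arm, 8 LAs | 7, 312 | 2.328, 0.240 | 0.032 to 0.351 |
| Pooled, arm removed | 14, 624 | 1.887, 0.400 | 0.045 to 0.240 |
| Pooled, arm and stratum removed | 13, 624 | 1.924, 0.384 | 0.044 to 0.248 |

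Worked example for the by-arm lower limit: 5.444 / 2.328 = 2.338, and (2.338 − 1) / (2.338 + 39) = 0.032.

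The interval width falls from 0.351 − 0.032 = 0.319 to 0.248 − 0.044 = 0.204, which is 36% narrower. As design effects (1 + 39 × ICC), the ranges are 2.3 to 14.7 by arm and 2.7 to 10.7 pooled with the stratum. If the by-arm fit also adjusted for the stratum (6 df), its interval would be 0.030 to 0.389, so the comparison above is the kinder one to the by-arm plan.

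**Sensitivity** (same formula; pooled means adjusted for arm and stratum):

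| Assumption changed | By arm | Pooled |
|---|---|---|
| Observed ICC 0.05 | 0.01 to 0.23 | 0.02 to 0.15 |
| Observed ICC 0.20 | 0.09 to 0.53 | 0.11 to 0.41 |
| 36 per LA (10% loss) | 0.03 to 0.36 | 0.04 to 0.25 |
| 24 per LA (60% followed up, the Table 8 threshold) | 0.02 to 0.37 | 0.04 to 0.26 |
| 12 LAs kept, 6 per arm (even loss assumed; 9 df pooled) | 0.03 to 0.44 | 0.04 to 0.30 |

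**Binary outcome.** The housing outcome is categorical, so the normal-theory interval is an approximation. In a simulation of binary data (beta-binomial, true ICC 0.10, 40 per LA), the central 95% of ICC estimates ran from 0.006 to 0.244 by arm and 0.026 to 0.202 pooled at an assumed prevalence of 20%. At 40% the ranges were 0.010 to 0.233 and 0.028 to 0.189. The pooled estimate removed the arm effect only. The ordering is the same.

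**The case against.** The strongest defence has four parts.

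- **By-arm reporting is legitimate.** Each intervention LA receives one nurse, which could change how much LAs differ in that arm, and the protocol describes usual outreach as varied between areas. Pooling assumes similar ICCs in the two arms. This stands, and it is why the by-arm values should be kept.
- **The pooled variance already exists.** The two-arm model estimates a common between-LA variance, adjusted for arm and funding. This also stands, but the protocol does not say that an ICC from it will be reported. The point is to name and report it.
- **The gain is modest.** A pooled interval of 0.04 to 0.25 is still too wide to size a trial with confidence, and the planned CIs will at least show the imprecision. This is correct. The limit is the 16 LAs.
- **Such detail can be left to the statistical analysis plan.** This holds for the estimator and its scale. It holds less well for the choice of by-arm estimation, which the protocol itself makes.

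Two stronger readings are tempting. First, a reader might infer that an imprecise by-arm ICC will be handed to the definitive trial and misdirect its size. The documents do not say so: the sentence in 10.4 on future sample size names the effect estimates, and 9.1 does not specify a by-arm ICC. Second, a reader might infer that the ICC will be on the wrong scale, because logistic and ordinal models give a latent-scale ratio while effects are to be reported as risk differences. The protocol does not state the scale, so this is something to clarify and not a fault.

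**Conclusion.** The point holds as a low-cost improvement. The only ICC estimation that the protocol specifies is by arm, from eight LAs each, although the ICC is a stated output and the stated model supports one estimate from all 16. At the planning values, pooling with adjustment for arm and stratum moves the 95% CI from about 0.03 to 0.35 to about 0.04 to 0.25.

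These figures are conditional. They assume an observed ICC of 0.10, equal LAs of 40, no loss and a normal-theory interval. They shift with the ICC, the follow-up and the number of LAs kept, but the pooled interval was the narrower one in every case checked. The pooled reading also rests on similar clustering in the two arms. Nothing here makes the by-arm ICCs wrong, and nothing affects the estimate of the intervention effect.

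**What to change.** In 10.4, state that one ICC per outcome will be estimated across both arms, adjusted for arm and RSI funding stratum, and reported with its 95% CI as the main ICC estimate for planning a definitive trial. Keep the by-arm ICCs as descriptive, so that readers can judge whether the assumption of similar clustering is reasonable. Where an ICC is reported, give its scale, and use the proportion scale for outcomes whose effects are risk differences.

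The cost is a sentence or two in the protocol and one further estimate per outcome from data already collected. The small downside is the assumption of similar ICCs in the two arms, which the by-arm values let readers check, though only roughly with eight LAs each.

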### 10.3. Analyses

As this is a pilot RCT, point estimates and 95% CIs will be presented but p-values for hypothesis testing will not. It is important that these tests are interpreted in the context that they are not fully powered such that a smaller effect would not suggest the intervention was ineffective. However, if the 95% CIs indicates significant benefit, then another trial would not be necessary.

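### Section 10.4 commits the pilot's effect estimate to sizing the definitive trial, although its standard error of 0.175 SD is too large to set a target difference

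*Protocol*

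**What the plan says.** The Primary Analysis section (10.4) of the protocol describes the housing model, the risk differences and relative risk ratios with 95% confidence intervals, and the ICCs by arm. It then says: "The effect estimates will be used for the sample size calculation of a future definitive study". ICCs are dealt with in the sentence before, so the effect estimates here are the intervention effects. The protocol names no minimum important difference and no rule for allowing for the estimate's uncertainty.

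Three other places bear on this:

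- Section 9.1 says the size of the pilot reflects what could be engaged in the time and budget available, and gives its operating figures: "The sample size was based on 80% power, 5% alpha, a minimum detectable effect size (MDES) of 0.53", with "an average cluster size (LA) of 40 service users" and an ICC of 0.1. Among the things the study will determine it lists "estimates of effect sizes and intra-cluster correlation coefficients".
- Section 10.3 says of the effect analyses that "they are not fully powered such that a smaller effect would not suggest the intervention was ineffective". It adds that no further trial is needed if the 95% confidence interval shows a significant benefit.
- Section 7.1 and Table 8 judge viability on recruitment, retention, data completeness, fidelity and acceptability. None of these criteria depends on the observed effect.

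**The concern.** A required sample size varies with one over the square of the target difference, so error in that difference is magnified in the size of the next trial. A pilot that over-estimates the effect yields a definitive trial smaller than it needs to be, which lacks its nominal 80% power. A pilot that under-estimates it yields a trial so large that a worthwhile service may never be tested.

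The ICC, the control-arm outcome distribution, cluster size and attrition are proper things to take from a pilot. The target difference is another matter. It should say what gain in housing would justify commissioning the service, and a study sized by budget cannot settle that. This is not a detail that the protocol leaves open for the statistical analysis plan: section 10.4 states the use that will be made of the estimate.

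**Working it through.** **Inputs.** From section 9.1 and Table 10: 16 clusters (8 per arm), 40 per cluster, 640 service users, ICC 0.10, 80% power, two-sided 5%, MDES 0.53, 10% attrition. Assumed, because the protocol gives no target for a definitive trial: true effects of 0.1, 0.2 and 0.3 SD. The ICC is treated as known.

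**1. Reproducing the plan's figures.**

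- Design effect = 1 + (40 − 1) × 0.10 = 4.9.
- SE of the standardised difference = √(4 × 4.9 / 640) = 0.175 SD.
- MDES with t on 14 df = (2.145 + 0.868) × 0.175 = 0.527, against 0.53 stated.
- 640 / 0.90 = 711.1, against 711 stated.

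The plan's arithmetic is sound. The question is how the estimate will be used.

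**2. Precision of the estimate.**

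- 95% CI half-width = 2.145 × 0.175 = 0.375 SD, or about 0.38.
- On a risk-difference scale with the same ICC, SE = √(p(1 − p)) × 0.175. For assumed proportions of 0.2 and 0.5 this is 0.07 and 0.0875, giving half-widths of 2.145 × 0.07 = 0.15 and 2.145 × 0.0875 = 0.19.

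**3. Size of a definitive trial planned on an estimate e.** With clusters of 40 and ICC 0.10, total clusters K = (2.80² × 4 × 4.9 / 40) / e² = 3.846 / e² (2.8016 before rounding). At 0.2 SD, 3.846 / 0.04 = 96.1, so about 97 clusters are needed. A trial planned on e when the truth is d has true power Φ(2.80 × d / e − 1.96). This is below 80% when e > d, and below 50% when e > 2.80 × d / 1.96.

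**4. Which pilots lead to a definitive trial.** Estimates at or below zero are set aside as unfavourable. Estimates above 0.375 are set aside because section 10.3 says a significant benefit makes another trial unnecessary. That leaves 0 < e < 0.375, with e distributed as Normal(d, 0.175).

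For d = 0.2:

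- P(0 < e < 0.375) = Φ(1.002) − Φ(−1.143) = 0.842 − 0.127 = 0.715.
- Share below 80% power = (0.842 − 0.500) / 0.715 = 48%.
- Share below 50% power (e > 0.286) = (0.842 − 0.688) / 0.715 = 21%.
- In simulation, the 10th and 90th percentiles of e are about 0.052 and 0.330. With K rounded up to an even number, these give about 1,440 and 36 clusters.

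For the other assumed effects:

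- d = 0.1: (0.942 − 0.500) / (0.942 − 0.284) = 67% below 80% power.
- d = 0.3: (0.667 − 0.500) / (0.667 − 0.043) = 27% below 80% power, or 26% once clusters are rounded up to an even number. None falls below 50%.

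**5. Sensitivity at d = 0.2, same selection.** The share below 80% power is 37% at ICC 0.05, 57% at ICC 0.20, 50% with 60% follow-up (24 per cluster) and 53% with 12 Local Authorities. The last two correspond to the lower edge of green in Table 8.

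**The case against.** The strongest reply is that the sentence is looser than a rule. It follows directly on estimates reported with 95% confidence intervals, and it does not say that the point estimate alone will be the target difference. The definitive trial would need its own justification, and nothing in the conduct or analysis of this pilot changes. That much is fair, and it limits how serious the point is. But the sentence is unqualified, and nothing else in the protocol supplies a target difference.

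Four stronger readings are tempting, and the documents do not support them.

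- A reader might infer that any positive estimate triggers a definitive trial, so that an ineffective service would go forward half the time. No such rule exists. Section 7.1 and Table 8 rest on feasibility, and an even chance of a positive estimate under no effect is a property of any symmetric unbiased estimator.
- A reader might infer that most trials planned this way would be underpowered. If every favourable estimate were carried forward, 57% at 0.2 SD and 52% at 0.3 SD would fall below 80% power. Section 10.3 removes the largest over-estimates, and the shares become 48% and 26%. A majority remains only for smaller effects.
- A reader might infer a systematic bias because only small trials get funded. The protocol gives no limit on an affordable size, so this cannot be put in figures.
- A reader might see a flat contradiction between sections 10.3 and 10.4. Section 10.3 calls the analyses not fully powered. It does not call the estimate uninformative.

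Section 9.1 lists effect sizes only as something to be estimated, so it needs no change.

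**Conclusion.** The point holds as a fault in one sentence of section 10.4. The protocol gives a design role to an estimate whose 95% confidence interval extends about 0.38 SD either side, and it states no minimum important difference. The main consequence is instability. At a true effect of 0.2 SD, trials planned on such estimates range from about 36 to 1,440 clusters when about 97 are needed. Nearly half (48%) miss 80% power, and about a fifth (21%) fall below 50%.

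These figures rest on assumed true effects, on the SD scale of Table 10 when the primary outcome is categorical, on a known ICC, and on the selection described in the working. Estimating the ICC from 16 clusters would add further error. The imprecision of the estimate does not depend on the assumed effects or on the selection: it follows from the plan's own inputs. The pilot's feasibility aims and its reporting of effects with confidence intervals are unaffected.

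**What to change.** Replace the sentence in section 10.4 with:

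> The sample size of a definitive trial will be based on a minimum important difference in 6-month housing situation, agreed with the funder and the TSC before the pilot's effect is known. The pilot will supply the control-arm outcome distribution, the ICC with its 95% CI, cluster size and attrition; the effect estimate's 95% CI will be used only to check whether that difference remains plausible.

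The cost is a short discussion with the funder and the TSC. It needs no new data and no change to the design or to the planned analyses. The timing matters, because the difference can be agreed without knowledge of the result only before the pilot's effect is seen.

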## Appendix C: Primary outcome measure: Housing Situation

**Which of these experiences best describes where you are staying now (please select only ONE option)?**

]

A) A place you own or rent (including with others)

1. You own (as the sole or joint owner).
2. Rent from a private landlord (where you are the sole or joint tenant).
3. Rent from your local council or housing association (where you are the sole or joint tenant).

B) Staying with others

4. Owned or rented by friends or family where you live on a long-term basis, but do not have a tenancy agreement.
5. Owned or rented by friends or family where you live on a short-term basis. This includes sofa surfing.

C) In some form of temporary or supported accommodation

6. Emergency accommodation provided by a local council or charity, such as space in a night shelter or B&B.
7. Temporary accommodation provided by or on behalf of your local council, such as a hostel.
8. Supported accommodation, for example where there is a staff member on site or on call, and you are expected to stay long-term.

D) Rough sleeping

9. Rough sleeping, on transport or in a transport hub (bus stop or train station), in a tent or car, or stairwells, barns, sheds, derelict boats or buildings.

E) Other options

10. A prison, probation facility, hospital, asylum support accommodation or similar.
11. Squatting, including with others.
12. Accommodation linked to your work or studies, for example student accommodation, military accommodation or accommodation linked to a business.

DK/NA

The data will be coded in three ways:

Level 1	Level 2	Level 3
Homeless	Rough sleeping	
 
● Rough sleeping, on transport or in transport hub (bus stop or train station), in a tent or car, or in stairwells, barns, sheds, derelict boats or buildings (D9)
 

	Temporary and/or unstable	
 
● Temporary accommodation provided by or on behalf of your local council, such as a hostel. (C7)
 
● Emergency accommodation provided by a local council or charity, such as space in a night shelter or B&B. (C6)
 

	Hidden	
 
● A place owned or rented by friends or family where you live on a short-term basis. This includes sofa surfing (B5).
 
● Squatting, including with others. (E11)
 

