Not homeless	Stable but insecure	
 
● A place owned or rented by friends or family where you live on a long-term basis, but do not have a tenancy or legal right. (B4)
 
● Accommodation linked to your work or studies (E12)
 
● Long-term accommodation classed as supported accommodation. (C8)
 

	Stable and secure	
 
● A place you own (where you are the sole or joint owner) (A1)
 
● A place you rent from a private landlord (where you are the sole or joint tenant) (A2)
 
● A place you rent from your local council or a housing association (where you are the sole or joint tenant) (A3)
 

Institution	Institution	
 
● A prison, probation facility, hospital or asylum support accommodation. (E10)
 

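### Level 3 housing situation is to be modelled as ordinal over A1 to E12, but the protocol never ranks these categories, and the questionnaire numbering it names can dilute or reverse the effect

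*Protocol*

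**What the plan says.** Protocol Section 10.4 summarises housing situation at three levels of detail and directs the reader onward: "See Appendix C for the coding of the outcomes". In that list Level 3 is called categorical, with no mention of order. The primary model is for Level 2 at 6 months.

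Later in the section Level 3 becomes ordinal: "For the categorical (ordinal) outcome of Level 3 all twelve categories (A1 to E12) will be included". The model is to be "fitted with the assumption of ordinal distribution, a logistic link function" and a random effect for Local Authority.

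The only ranking in the document is a four-step one in the same section ("1=stable but secure), (2=stable but insecure), (3=hidden, temporary and/or unstable), (4=rough sleeping"). It is introduced there as the Level 1 outcome, although its categories are those of Level 2 with hidden and temporary merged.

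Appendix C numbers the options 1 to 12 under letters A to E. A separate table then assigns each option to a Level 2 and a Level 1 class.

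For anyone in an institution at follow-up, Section 10.4 substitutes the previous housing situation, at every level of categorisation.

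**The concern.** An ordinal logistic model needs a ranking of its categories. The protocol commits to the model and names a set of codes, but gives no ranking of that set. The one sequence it names, A1 to E12, is the order in which the options appear on the form, and that order does not run from better to worse housing.

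If the codes were used as they stand, someone moving from a hostel (C7) to long-term supported accommodation (C8), or from the street (D9) to work-linked accommodation (E12), would be scored as having got worse. The common odds ratio would mix correctly and wrongly directed moves. It would be reported beside the Level 1 and Level 2 results under the heading of the primary analysis, in a section that says the effect estimates will inform the sample size of a definitive trial.

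The count of twelve is also wrong on the section's own terms, because the institution rule removes E10 before analysis.

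**Working it through.** The protocol states no figure for Level 3, so there is nothing to reproduce. The check has two parts: one uses the documents alone, the other uses assumed distributions.

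**1. Code order against the protocol's own classes (no assumptions about data).** E10 is left out because the institution rule empties it.

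- Not homeless (Appendix C): A1, A2, A3, B4, C8, E12, which is 6 codes.
- Homeless: B5, C6, C7, D9, E11, which is 5 codes.
- Between-class pairs: 6 × 5 = 30. The not-homeless code carries the higher number in 8 of them: C8 against B5, C6 and C7 (3 pairs), and E12 against B5, C6, C7, D9 and E11 (5 pairs).
- On the four-step ranking the steps hold 3, 3, 4 and 1 codes. Between-step pairs: 3×3 + 3×4 + 3×1 + 3×4 + 3×1 + 4×1 = 43. Of these, 9 are inverted: the 8 above plus E11 against D9.

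**2. Effect on the odds ratio.** The model is logit P(Y ≤ k) = θ_k − β × arm, with higher codes worse, so exp(β) is the odds ratio for a worse category. The fits are to population percentages, without cluster effects or sampling error. The documents give no expected category proportions, so both control distributions below are assumptions.

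*Distribution I*, control, in order A1, A2, A3, B4, B5, C6, C7, C8, D9, E10, E11, E12 (%): 0, 4, 4, 2, 8, 12, 15, 8, 42, 3, 1, 1. Not homeless = 4 + 4 + 2 + 8 + 1 = 19%. For the four-step fit, E10 is carried to rough sleeping.

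*Distribution II*, control (%): A2 2, A3 4, B4 2, B5 5, C6 10, C7 20, C8 10, D9 44, E11 2, E12 1. Not homeless = 2 + 4 + 2 + 10 + 1 = 19%.

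| Distribution | Change in the intervention arm | OR worse, A1–E12 order | OR worse, four-step ranking |
|---|---|---|---|
| I | 12 points B5/C6/C7 to C8 (4 from each); not homeless 19% to 31% | 1.21 | 0.82 |
| I | 12 points D9 to C8 | 0.83 | 0.59 |
| I | 12 points D9 to C6/C7 | 0.72 | 0.71 |
| II | 15 points C6/C7 to C8; not homeless 19% to 34% | 1.22 | 0.77 |
| II | 5 points D9 to E12; not homeless 19% to 24% | 1.08 | 0.80 |
| II | 5 points D9 to C7 plus 15 points C6/C7 to C8 | 1.06 | 0.67 |
| II | 10 points D9 to C7 | 0.76 | 0.75 |
| II | 10 points D9 to C8 | 0.84 | 0.64 |
| II | 5 points D9 to A3 plus 5 points D9 to C7 | 0.69 | 0.67 |

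The sign reverses where the net gain is movement into C8 from B5, C6 or C7, or movement into E12. It is diluted but kept for D9 to C8, and almost unchanged for D9 to C6, C7 or A3.

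**3. A different order.** The Appendix C coding table lists the codes as D9; C7, C6; B5, E11; B4, E12, C8; A1, A2, A3; then E10. Read from worst to best, with E10 carried to D9, the first row of Distribution I gives 0.83, close to the four-step 0.82. So the reversal comes from the questionnaire numbering, not from modelling the detailed categories as such.

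**The case against.** The strongest reply is that the protocol never says the option number is the rank. On this reading A1 to E12 only names which categories enter the model. The coding table in Appendix C, to which Section 10.4 refers, lists the classes from worst to best apart from the final institution row, and an analyst following it would get the right direction (0.83 above). Section 10 calls itself a brief overview with a detailed analysis plan to follow. The reversal example also holds rough sleeping at 42% in both arms, although the intervention aims at exits from the street, and direct exits mostly keep their sign. Level 3 is not the primary model, no p-values will be reported, and the main pilot outcome is the feasibility criteria.

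Most of this stands. A reader might infer that the planned analysis will report benefit as harm, or that its odds ratio would have no meaning. The documents support neither: questionnaire order is an inference, and even under it the estimate points the right way for most moves off the street.

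Two things remain. First, the choice of an ordinal model is fixed in the protocol, and no complete order of its categories can be taken from the document. The table is not presented as a ranking, and within a class the two available sequences conflict. Read from worst to best, the table puts home ownership (A1) below council or housing association tenancy (A3), whereas the numbering puts it above. Second, the planned evaluation of model assumptions is no safeguard, because a fit check cannot establish that the order of categories is meaningful.

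The E10 conflict is a matter of wording. An emptied category does not disturb an ordinal fit, but the stated count is still inconsistent with the institution rule.

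**Conclusion.** The point holds as a moderate issue. The protocol prescribes an ordinal model for a set of categories that it does not rank. The one sequence it names contradicts its own homeless/not-homeless coding in 8 of 30 pairs and its four-step ranking in 9 of 43. If that sequence were used, the odds ratio could be diluted (0.83 against 0.59 for D9 to C8) or reversed (1.21 against 0.82 for B5/C6/C7 to C8). The pair counts rest on the documents alone. The odds ratios rest on assumed distributions and on the numbering being used as the rank.

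It would be wrong to conclude that the primary result is at risk. The primary model is for Level 2, and the Level 1 model is binary; neither depends on the order of the Level 3 codes.

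**What to change.** Remove the sentences in Section 10.4 that fit an ordinal model to Level 3. Report Level 3 only as the frequencies and proportions that the section already plans, shown by arm and time point. Confine modelling to Level 2, in the four-step order of Section 10.4 (now labelled there as Level 1), and to Level 1.

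If a Level 3 model is kept, state its ranking before analysis, consistent with the Level 1 and Level 2 grouping in Appendix C. Collapse categories within a Level 2 class that have no defensible order, and remove E10 from the set. Full collapsing leads back to Level 2, which is a further reason to drop the model.

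The cost is a few lines of text and one fewer modelled result. The detailed picture of where people are living is kept in the descriptive tables.
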